1.3 Study Design

This is a Phase II open-label study in NSCLC patients with oligometastatic disease (defined here as 1-3 observable metastases after the completion of chemotherapy) who have no evidence of disease progression after standard first-line therapy (4-6 cycles of platinum-doublet chemotherapy, with or without bevacizumab; erlotinib or crizotinib alone or in combination with other regimens are also acceptable options for patients with tumors known to bear a known EGFR activating mutation (for erlotinib or afatinib) or EML4ALK fusion (for crizotinib). Patients will be enrolled either prior to completing 4 cycles of induction

chemotherapy (step 1 enrollment) or after the completion of at least 4 cycles of chemotherapy (step 2 enrollment). In either case, they will be randomized during Step 2 to the “immediate LCT” arm consisting of LCT followed by either surveillance or maintenance therapy at the discretion of the treating physician, compared to delayed/no LCT. When undergoing LCT (in either arm), patients will receive consolidative therapy with either radiotherapy or surgery for all residual lesions (primary and metastases). The choice of the specific consolidative therapy will be made by the treating physician(s). Consultation with a multidisciplinary team including a radiation oncologist and thoracic surgeon is encouraged.

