7.4 Design

Design Assumptions:

Primary endpoint	Progression-free survival (PFS)
Null hypothesis	Median PFS equals to 4 months in both groups
Alternative hypothesis	Median PFS equals to 4 months in the delayed/no LCT group and equals to 7 months in the immediate LCT group.
Associated hazard ratio	0.57 = 75% improvement in median PFS
Type I error	10%
Type II error	10%
Accrual rate	2-3 patients/month
Follow-up	9 months

A design with one-sided 10% type I error and 90% power would require an expected number of progression events of 87 under the alternative hypothesis to detect 75% improvement in median PFS. Given these assumptions, this design would require 94 patients *randomized* over 37.6 months with additional 9 months of follow-up. One interim analysis will be performed to allow for the early termination of the trial in light of evidence that the LCT arm is superior to the no LCT arm or there is no difference between the two treatment arms. In order to provide an overall significance level of 0.05 for the study, the interim analysis will use a Lan-DeMets monitoring boundary with an O'Brien-Fleming stopping rule (East 5.4.2.0, Cytel 2011). The interim analysis will be performed when 44 out of the expected 87 events have been observed. Using O'Brien-Fleming test boundaries, the Z-score test cut-off at the interim analysis for stopping and rejecting the null hypothesis will be 2.054, the Z-score test cut-off at the interim analysis for stopping and rejecting the alternative (futility) is -0.203.

In order to obtain 94 patients for randomization, we estimate that 25% of patients (24) will undergo progression of disease during induction chemotherapy based on the first 6 months of patient enrollment. In addition, we anticipate that 20% of patients (19) will refuse randomization after up-front systemic therapy. Therefore, in order to randomize 94 patients, we anticipate that we will need to enroll $94 + 24 + 19 = 137$ patients. Note that patients who cross-over to the alternative treatment arm due to toxicity will be censored at the time of crossover, with the last progression-free date being the date of crossover.

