7.6 Off-study criteria

Patients who enroll on Step 1 will be followed for survival status prior to step 2 if they: 1) progress on chemotherapy, 2) experience toxicity that is deemed to be unacceptable by the treating physician prior to the minimum requirements for induction chemotherapy (i.e. 4 cycles of platinum doublet therapy, 3 months of erlotinib/ afatinib, or 3 months of crizotinib), or 3) refuse randomization. If this occurs, they will remain on study only until proceeding to LCT at the end of induction chemotherapy, if applicable (e.g. without any maintenance therapy or second line systemic therapy), and will be followed for survival status at the conclusion of LCT. Allowing patients to remain on study until the time of LCT will allow for tissue collection if the patient proceeds to surgical resection. Patients who do not proceed with randomization but do not proceed immediately to LCT (receiving maintenance therapy or further systemic therapy) will be followed for survival status immediately after proceeding to maintenance therapy or further systemic therapy.

Patients who continue to step 2, or enroll at step 2, will be followed for survival status at the time of RECIST progression. Patients that are randomized to the immediate LCT arm will be followed for survival status immediately after experiencing RECIST progression. Patients that are randomized to the delayed LCT arm that experience progression will remain on study until the completion of LCT *only if LCT is planned within 6 weeks*. In this scenario, the patient will be followed for survival status at the conclusion of LCT. If no LCT is planned within this timeframe (i.e. if second line chemotherapy is planned and not LCT), the patient will be followed for survival status immediately after experiencing RECIST progression. Allowing patients to remain on study until the time of LCT will allow for tissue collection at that time if the patient proceeds to surgical resection. At that time, crossover can occur between treatment arms, at the treating physician's discretion. Crossover can also occur due to treatment toxicity or an increase in the size of disease that does not meet the criteria of RECIST progression. Patients who do not meet the criteria for RECIST progression and crossover to the alternate arm (e.g., crossover for a reason other than progression) will remain on study and will be followed for survival status.

8. Evaluation of Outcomes of Interest

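### The enrolment figure of 137 takes the 25% and 20% losses from the 94 randomised rather than from those enrolled; at the stated rates about 157 are needed if all enter at Step 1.

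*Combined protocol and SAP*

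**What the plan says.** Section 7.4 fixes the size of the randomised comparison: "this design would require 94 patients *randomized* over 37.6 months with additional 9 months of follow-up", with 87 expected events, one-sided 10% type I error and 90% power for median PFS of 4 against 7 months.

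It then works back to enrolment using two losses. On the first, "we estimate that 25% of patients (24) will undergo progression of disease during induction chemotherapy based on the first 6 months of patient enrollment". On the second, "we anticipate that 20% of patients (19) will refuse randomization after up-front systemic therapy". The conclusion is that "in order to randomize 94 patients, we anticipate that we will need to enroll $94 + 24 + 19 = 137$ patients".

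Section 7.6 shows where these losses fall: "Patients who enroll on Step 1 will be followed for survival status prior to step 2 if they: 1) progress on chemotherapy". The same list includes refusal of randomisation, and also unacceptable toxicity before minimum induction is complete.

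There is a second way in. Section 1.3 allows enrolment after at least four cycles of chemotherapy, and Section 7.6 recognises it: "Patients who continue to step 2, or enroll at step 2, will be followed for survival status at the time of RECIST progression". Section 3.1.1.8 requires Step 2 patients to be free of RECIST progression. No section states what share is expected to enter by this route.

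**The concern.** The counts 24 and 19 are percentages of the 94 who reach randomisation. A randomised patient cannot have been lost before randomisation, so 94 is the wrong base. The 25% is said to come from the first six months of enrolment, which also points to a denominator of enrolled patients.

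In the text available, 137 is the only enrolment figure. If it is a forecast, it may understate how many patients must consent and be followed through induction. If it is treated as a limit, the trial could close short of 94 randomised and 87 events. The plan does not say which it is.

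**Working it through.** **Inputs.** From Section 7.4: 94 randomised; 25% progressing during induction; 20% refusing after up-front therapy; 137 enrolled; medians of 4 and 7 months (HR 4/7); one-sided 10% type I error; 37.6 months of accrual plus 9 of follow-up. From Section 4.0: 1:1 allocation. Not given in the documents: the share *s* entering directly at Step 2.

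**1. Reproducing 137.** 0.25 × 94 = 23.5, rounded to 24. 0.20 × 94 = 18.8, rounded to 19. 94 + 24 + 19 = 137. The figure reproduces with 94 as the base.

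**2. Rates implied by the printed counts.** Progressing: 24/137 = 17.5%. Refusing among the remainder: 19/(137 − 24) = 19/113 = 16.8%. These are not 25% and 20%.

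**3. All patients entering at Step 1.**
- Losses in sequence, with the 20% applied to those who finish induction: 94/(0.75 × 0.80) = 156.7, so 157 enrolled. The yield from 137 is 137 × 0.60 = 82.2 randomised.
- Both rates read as shares of all enrolled: 94/(1 − 0.45) = 170.9, so 171 enrolled. The yield from 137 is 137 × 0.55 = 75.

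The first reading fits the wording on refusal better and is used below.

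**4. Allowing for direct Step 2 entry.** Assume direct entrants have no induction loss and that 25% is the Step 1 rate.
- (A) 20% refusal on both routes: N = 94/(0.80 × [0.75(1 − s) + s]).
- (B) Only Step 1 patients refuse: N = 94/(0.60(1 − s) + s).

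| s | A: needed | A: yield of 137 | B: needed | B: yield of 137 |
|---|---|---|---|---|
| 0 | 156.7 | 82.2 | 156.7 | 82.2 |
| 0.20 | 146.9 | 87.7 | 138.2 | 93.2 |
| 0.40 | 138.2 | 93.2 | 123.7 | 104.1 |

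The share at which 137 is just enough:
- A: s = (94/(137 × 0.80) − 0.75)/0.25 = 0.43
- B: s = (94/137 − 0.60)/0.40 = 0.22

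**5. Consequence if enrolment stopped at 137.** With exponential PFS, rate λ = ln 2/median, uniform accrual over T = 37.6 months and F = 9 months of further follow-up, the event probability is 1 − (e^(−λF) − e^(−λ(T+F)))/(λT). This gives 0.968 for a 4-month median and 0.892 for a 7-month median, mean 0.930. Expected events are 94 × 0.930 = 87.4, which agrees with the plan's 87.

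Power = Φ(√(D/4) × |ln(4/7)| − 1.2816). Here D is the number of events multiplied by 83.9/87, where 83.9 is the Schoenfeld requirement at 90% power; this allows roughly for the interim analysis.

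| Randomised | Expected events | Power |
|---|---|---|
| 94 | 87.4 | 90.1% |
| 87.7 (s = 0.20, A) | 81.6 | 88.5% |
| 82.2 (s = 0) | 76.5 | 86.9% |

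If accrual instead stays at 94/37.6 = 2.5 a month, 82.2 patients take 32.9 months. About 75.7 events are then expected and power is 86.6%.

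**The case against.** The best defence is that 137 is only a forecast. Section 7.4 uses the language of anticipation, the design requirement is stated as patients randomised, and no section says that enrolment stops at 137. That is fair. It means the power loss is conditional, and even in the all-Step-1 case it is only about three percentage points. It does not make the forecast follow from its own rates.

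The second defence is direct Step 2 entry. Section 7.6 lists refusal among the outcomes of Step 1 enrollees, and Section 3.1.1 combines Step 2 enrolment with randomisation. Both lean towards (B), where 20% direct entry already yields about 93 randomised. With the share unstated, 137 could turn out to be enough. But Section 7.4 does not mention the route in its calculation and applies the 25% to patients in general, so if 137 sufficed it would be by coincidence.

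Two limits on the corrected figures also stand:
- The formulas with *s* assume that 25% is the Step 1 rate. If the observed 25% already mixes both routes, they credit direct entry twice and give too small a number.
- Section 7.6 names unacceptable toxicity during induction as a further Step 1 loss, and Section 7.4 gives no rate for it. So 157 is what the two stated rates imply, not a complete forecast, and a toxicity loss would raise it.

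**Conclusion.** The point holds. With all patients at Step 1 and losses in sequence, 137 falls short by about 20 enrolled patients (157/137 is about 15% more), or by about 12 randomised (82 against 94). The gap narrows as direct Step 2 entry rises and closes at a share between about 22% and 43%, depending on whether direct entrants can refuse.

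This is an error in the recruitment projection. It does not touch the endpoint, the test or the 94 and 87 targets. Events and power suffer only if enrolment is cut off at 137 with too little direct entry. It should be corrected because a headline planning figure contradicts the rates printed beside it and the correction is easy.

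**What to change.** In Section 7.4, replace the sum with a loss calculation that gives the base of each rate and the expected share *s* entering directly at Step 2. Use formula (A) if refusal applies to both routes, or (B) if only Step 1 patients can refuse. With s = 0 the result is about 157. State whether the 25% was observed among Step 1 entrants only; if it was not, the formula must be adapted. Also say whether a loss to toxicity during induction is allowed for.

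Add one sentence: enrolment continues until 94 patients are randomised. If 137 is meant as a limit, say so, and restate the expected number randomised, the events and the power for the assumed *s*.

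The cost is one or two corrected sentences and one stated assumption, which the early enrolment data should inform. The forecast enrolment probably becomes less favourable or, if 137 is a limit, the stated power may.

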7.5 Statistical Analysis Plan

Descriptive statistics will be provided to summarize the patient characteristics and toxicities by the treatment arms (immediate LCT and delayed/no LCT groups). Chi-square test or Fisher's exact test will be applied to compare patient characteristics between the two arms. The balance of the five prognostic covariates (used in the Pocock-Simon's dynamic allocation method) between the two arms will be examined as well. For the primary endpoint, PFS, Kaplan-Meier estimate will be computed, and the log-rank test will be performed to compare the difference of PFS between the two arms. Cox regression model will be applied to correlate PFS with potential covariates in both the univariate and multi-covariate analyses. Patients are considered evaluable for efficacy if they receive at least one of the intended local consolidation therapy. Both the intent-to-treat analysis and analysis among the evaluable patients will be performed. The corresponding results will be compared and contrasted. For the secondary endpoints, similar analysis will be performed on the overall survival and other time-to-event endpoints. Safety and tolerability of the immediate LCT arm and delayed/no LCT arm will be summarized by descriptive statistics. Quality of life will be analyzed by the repeated measures analysis of variance to count for the change before and after treatment and during the follow-up period. Proper transformation will be performed if necessary to transform data to be closer to the Gaussian distribution. All the statistical analyses will be two-sided with a P-value of 0.10 or less considering statistically significant.

Note that the MDACC DSMB will be providing study-wide oversight in regards to the endpoints described above.

To account for patients that crossover for reasons other than RECIST progression of disease (e.g. toxicity, growth of the malignancy that does not constitute RECIST progression), censoring will occur at the time of crossover for our primary analysis. In addition, a secondary time varying covariate Cox model analysis will be done to assess the impact of crossover without RECIST progression.

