1.2 Secondary Objectives

The secondary objectives of this study will be to:

- Determine the overall survival
- Safety/tolerability of LCT
- Time to progression of prior metastatic lesions
- Time to appearance of new metastases (CNS vs. extra-CNS, treated lesion vs. new site)
- Quality of life

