4.0 Treatment Plan

Prior to randomization, eligible patients will have received 4-6 cycles of induction chemotherapy, erlotinib or afatinib (for patients with known EGFR mutations) or crizotinib (for patients with known EML4-ALK fusion) without evidence of RECIST progression. They will be registered and then randomized in a 1:1 fashion to either immediate or no/delayed LCT. All patients will be followed until progression of disease is documented or two years after randomization, whichever comes first. Patients with metastases involving the brain or spinal cord, or metastatic lesions causing symptoms requiring palliation (e.g., bone, soft tissue) may be treated with surgery or radiotherapy prior to the completion of induction chemotherapy (randomization).

The following imaging studies are suggested after first-line therapy to assess the number of sites: 1) imaging of the brain with either a magnetic resonance imaging (MRI) scan (preferred) or a CT scan of the brain with contrast, and 2) systemic imaging with a positron emission tomography/computed tomography (PET/CT) scan or a CT scan of the chest/abdomen/pelvis with contrast. Other studies, such as a bone scan, and aspiration of pleural fluid, are at the treating physician's discretion.

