C) Quality of life multiple-symptom assessment pool- see section 5B above.

7. Statistical Considerations

7.1 Preliminaries. The purpose of this study is to test the hypothesis that the treatment paradigm of immediate LCT after induced oligometastatic disease can lead to reduced rates of disease progression. Patients will be randomized between immediate LCT and delayed/no LCT arms. The primary outcome will be progression-free survival (PFS) time, defined as the time from the time of randomization (immediate LCT vs. delayed/no LCT) to disease progression or death. The primary goal will be to compare the PFS times of these two arms.

7.2 Database Used for Collection. Study data will be collected and managed using REDCap (Research Electronic Data Capture) electronic data capture tools hosted at MD Anderson. [ref] REDCap (www.project-redcap.org) is a secure, web-based application with controlled access designed to support data capture for research studies, providing: 1) an intuitive interface for validated data entry; 2) audit trails for tracking data manipulation and export procedures; 3) automated export procedures for seamless downloads to common statistical packages; and 4) procedures for importing data from external sources. In the case of multi-center studies REDCap uses Data Access Groups (DAGs) to ensure that personnel at each institution are blinded to the data from other institutions. REDCap (<https://redcap.mdanderson.org>) is hosted on a secure server by MD Anderson Cancer Center's Department of Research Information

Systems & Technology Services. REDCap has undergone a Governance Risk & Compliance Assessment (05/14/14) by MD Anderson's Information Security Office and found to be compliant with HIPAA, Texas Administrative Codes 202-203, University of Texas Policy 165, federal regulations outlined in 21CFR Part 11, and UTMDACC Institutional Policy #ADM0335. Those having access to the data file include the study PI and research team personnel. All protected health information (PHI) will be removed from the data when it is exported from REDCap for analysis. All dates for a given patient will be shifted by a randomly generated number between 0 and 364, thus preserving the distance between dates. Dates for each patient will be shifted by a different randomly generated number. Following publication study data will be archived in REDCap.

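### Section 7.5 names no competing-risks method for prior-lesion progression and new metastases, so one minus Kaplan-Meier would overstate how often each occurs

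*Combined protocol and SAP*

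**What the plan says.** Section 1.2 lists among the secondary objectives "Time to progression of prior metastatic lesions" and "Time to appearance of new metastases (CNS vs. extra-CNS, treated lesion vs. new site". Neither is defined further: event, competing events and censoring are not stated.

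Section 7.5 sets the primary method: "For the primary endpoint, PFS, Kaplan-Meier estimate will be computed, and the log-rank test will be performed", with Cox regression for covariates. For the secondary endpoints it says that "similar analysis will be performed on the overall survival and other time-to-event endpoints". No cumulative-incidence or other competing-risks method appears anywhere in the document.

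Section 7.1 defines PFS as the time from randomization "to disease progression or death", so death is an event for the primary endpoint.

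On follow-up, section 4.0 says: "All patients will be followed until progression of disease is documented or two years after randomization, whichever comes first". Section 7.6 adds that patients in step 2 "will be followed for survival status at the time of RECIST progression", and for one arm specifically: "Patients that are randomized to the immediate LCT arm will be followed for survival status immediately after experiencing RECIST progression". The one exception is a delayed-arm patient whose LCT is planned within 6 weeks of progression. That patient stays on study until LCT is complete.

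**The concern.** Kaplan-Meier suits PFS because progression and death are both events, so nothing competes with the endpoint. That does not carry over to a single type of failure. A patient who dies without prior-lesion progression can no longer have it. A patient whose first RECIST progression is a new metastasis generally leaves disease follow-up, so later progression of a prior lesion is usually not seen.

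If both kinds of patient are censored, Kaplan-Meier treats them as having the same future risk as those still under observation. One minus the estimate (1 − KM) is then not the probability of that failure type, but something larger. Curves for the separate types can add to more than the total failure rate. The excess also depends on the overall hazard, so it differs between arms if LCT works as planned.

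These endpoints are meant to show whether LCT controls existing disease or delays new disease. Inflated absolute risks, inflated unequally by arm, would blur that picture.

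**Working it through.** **Inputs from the plan (section 7.4).** Median PFS is 4 months (delayed/no LCT) and 7 months (immediate LCT), with 94 patients, 37.6 months of accrual, 9 months of further follow-up and 87 expected events.

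**The plan's own figure.** It states no incidence for the two secondary endpoints, so the only check is on the PFS model. With exponential PFS, λ = ln 2/median, A = 37.6 and F = 9, the probability of an event is 1 − [exp(−λF) − exp(−λ(A+F))]/(λA).

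- Delayed/no LCT: λ = 0.1733, probability 0.968.
- Immediate LCT: λ = 0.0990, probability 0.892.
- Expected events: 47 × (0.968 + 0.892) = 87.4, which agrees with 87.

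Constant hazards at these medians are therefore consistent with the plan's design.

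**Assumption.** The documents do not split first events by type. I assume 40% prior-lesion progression, 40% new metastasis and 20% death, the same in both arms. Let s be the share of one failure type and d the share of death.

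**Formulas**

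- 1 − KM, other first failures and deaths censored: 1 − exp(−sλt)
- Cumulative incidence, death and other first failures competing: s × [1 − exp(−λt)]
- Cumulative incidence, only death competing: s/(s+d) × [1 − exp(−(s+d)λt)]

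**At t = 12 months, s = 0.4, d = 0.2**

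Delayed/no LCT, where exp(−λt) = 2^(−3) = 0.125:
- 1 − KM = 1 − 2^(−1.2) = 56.5%
- All competing: 0.4 × 0.875 = 35.0%
- Only death competing: (0.4/0.6) × (1 − 2^(−1.8)) = 47.5%

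Immediate LCT, where exp(−λt) = 2^(−12/7) = 0.305:
- 1 − KM = 1 − 2^(−0.686) = 37.8%
- All competing: 0.4 × 0.695 = 27.8%
- Only death competing: (0.4/0.6) × (1 − 2^(−1.029)) = 34.0%

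**Coherence.** In the delayed/no LCT arm the two failure types have 1 − KM values that add to 2 × 56.47 = 112.9%, although only 87.5% of patients have had any PFS event.

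**Arm difference for one endpoint.** By 1 − KM it is 56.47 − 37.83 = 18.6 points. By cumulative incidence it is 35.0 − 27.8 = 7.2 points with all competing, and 47.5 − 34.0 = 13.5 points with only death competing.

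**Sensitivity to the split.** Five assumed splits (prior lesion/new metastasis/death) were tried: 45/45/10, 40/40/20, 30/40/30, 20/60/20 and 60/20/20. The 12-month excess of 1 − KM over cumulative incidence is:

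| Competing events | Delayed/no LCT | Immediate LCT |
|---|---|---|
| Death and other first failures | about 17 to 21 points | about 7 to 10 points |
| Death only | about 5 to 13 points | about 2 to 6 points |

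**Simpler model.** Put one failure type against everything else, with share s. In the delayed/no LCT arm the excess is:
- s = 0.3: 46.4 − 26.25 = 20.2 points
- s = 0.5: 64.6 − 43.75 = 20.9 points
- s = 0.7: 76.7 − 61.25 = 15.4 points

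The range is 15 to 21 points, and the same shares give 8 to 10 points in the immediate LCT arm.

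**The case against.** Several points on the other side stand.

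- **Only death truly precludes these events.** A reader might infer that prior-lesion progression and new metastasis exclude each other. They do not: either can follow the other, and both can appear on one scan, since section 8 has primary and metastatic sites evaluated together. They compete here only because disease follow-up generally ends at RECIST progression.
- **The size depends on the quantity wanted.** The larger gap applies to type of first failure. If the target is the event at any time before death, only death competes and the gap roughly halves or better. The plan does not say which is meant.
- **The tests are not at fault.** A reader might infer that log-rank and Cox are invalid here. With other events censored they compare cause-specific hazards correctly. In the model above that hazard ratio is 4/7 for each type, whatever the split.
- **The reading is inferred.** The plan states no incidences for these endpoints and does not say that deaths are censored.
- **The weight is limited.** These are secondary endpoints in a 94-patient phase II trial.

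What does not stand is the reply that this is only missing detail. The section points to a particular estimator, and that estimator overstates incidence under either choice of competing events. Counting deaths as events would not rescue it, because the curve would then mix deaths with lesion progression. Nor is it safe to read 1 − KM as risk in a world without the other failures. That needs progression at one site to be independent of progression elsewhere in the same patient, which is not plausible.

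**Conclusion.** The point holds for the incidence estimates of the two failure-type endpoints. On the natural reading of section 7.5, 1 − KM overstates how often each type occurs. In every assumed split, with constant hazards at the plan's medians, the 12-month excess is larger in the delayed/no LCT arm, so the absolute difference between arms is overstated as well.

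The direction is firm. The size is illustrative: it rests on constant hazards, on shares that the documents do not give, and on equal shares in both arms, although LCT may change the pattern of failure. The death-only figures also assume that hazards do not change after a first progression elsewhere.

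A reader might go further and conclude that the main result is affected. The documents do not support that: PFS counts death as an event, and the 87 events, 94 patients and interim boundaries do not depend on these endpoints. Nor is it certain that published incidences will be too high. That follows only if 1 − KM is reported as the probability of the event.

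**What to change.** In section 7.5, take these two endpoints out of the sentence on similar analysis and specify them separately:

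1. Define the event, the competing events and the censoring for each, including whether censoring at non-progression crossover, stated for the primary analysis, applies here.
2. Report Aalen-Johansen cumulative incidence by type of first failure: prior metastatic lesion, primary or nodal disease, new CNS metastasis, new extra-CNS metastasis. Keep the treated-lesion versus new-site split of section 1.2. Treat death and the other first-failure types as competing events. Primary or nodal progression needs its own category because it is also RECIST progression and ends disease follow-up.
3. Give a rule for classifying failures of more than one type found on the same scan.
4. Compare arms by cause-specific log-rank and Cox, with Gray's test as a supplement.
5. State that only the first failure type is generally observed, because disease follow-up ends at RECIST progression.

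The cost is SAP wording and a little more programming. No added patients or visits are needed, provided that the type of first progression is recorded, which these endpoints already require. The downside is that absolute differences between arms will probably look smaller than they would from Kaplan-Meier curves.
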